12.5.2 Safety endpoints

For all safety analyses, the safety set will be used. All listings and tables will be presented by group. If the Phase I preliminary dose is different to RP2D, the safety data will be listed and summarized by age group and dose level. For safety evaluations (except for AE), the last available assessment on or before the date of start of study treatment is taken as the “baseline” assessment.

Safety summaries (tables, figures) include only data from the on-treatment period with the exception of baseline data which will also be summarized where appropriate (e.g. change from baseline summaries). In addition, a separate summary for death including on treatment and post treatment deaths will be provided. In particular, summary tables for (AEs) will summarize only on-treatment events, with a start date during the on-treatment period (*treatment-emergent* AEs).

The on-treatment period lasts from the date of first administration of study treatment to 30 days after the date of the last actual administration of any study treatment.

Adverse events

All information obtained on adverse events will be displayed by group for all patients on safety set.

The number (and percentage) of patients with treatment emergent adverse events (events started after the first dose of study medication or events present prior to start of study treatment but increased in severity based on preferred term) will be summarized in the following ways:

- by group, primary system organ class and preferred term.
- by group, primary system organ class, preferred term and maximum severity (based on CTCAE grades).
- by group, Standardized MedDRA Query (SMQ) and preferred term

Separate summaries will be provided for study medication related adverse events, death, serious adverse events, other significant adverse events leading to discontinuation.

The number (and proportion) of subjects with adverse events of special interest (AESI) such as worsening cytopenias, infections etc. during the on-treatment period will be summarized by group.

All deaths (on-treatment and post-treatment) will be summarized.

All AEs, deaths and serious adverse events (including those from the pre and post-treatment periods) will be listed and those collected during the pre-treatment and post-treatment period will be flagged.

The proportion of patients developing Grade 2 to 3 infections using infection severity ([Section 16.1](#) Appendix 1) during the aGvHD treatment period Day 1 to Day 56 will be summarized in addition to standard CTCAE grading. In addition, proportion of patients developing second primary malignancies will be summarized based on the entire study period. A subject with multiple adverse events within a primary system organ class is only counted once towards the total of the primary system organ class.

Vital signs

All vital signs data will be listed by group, patient, and visit/time and if ranges are available, abnormalities will be flagged. Summary statistics will be provided by group and visit/time.

Clinical laboratory evaluations

All laboratory data will be listed by group, patient, and visit/time and if normal ranges are available abnormalities will be flagged. Shift tables using the low/normal/high/ (low and high) classification will be used to compare baseline to the worst on-treatment value.

Tolerability

The number and percentage of patients who have a dose increase, reduction, or interruption will be summarized.

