
Key Secondary To assess the rate of durable ORR at Day 56To estimate ORR at Day 14To assess pharmacokinetic/pharmacodynamic relationshipsTo assess Duration of responseTo assess the cumulative steroid dose until Day 56To evaluate the safety and tolerability of ruxolitinibTo assess Overall Survival (OS)To assess Event-Free Survival (EFS)	
Proportion of all patients who achieve a CR or PR at Day 28 and maintain a CR or PR at Day 56Proportion of patients who achieved ORR (CR+PR) at Day 14PK parameters (such as AUC, Cmax, Ctrough) versus safety, efficacy, and PD biomarkers, as appropriateDuration of response (DOR) is assessed for responders only and is defined as the time from first response until aGvHD progression or the date of additional systemic therapies for aGvHD. Onset of chronic GvHD, or death without prior observation of aGvHD progression are considered as competing risksWeekly cumulative steroid dose for each patient up to Day 56Safety and tolerability including myelosuppression, infections, and bleeding will be assessed by monitoring the frequency, duration and severity of Adverse Events including occurrence of any second primary malignancies, infections, by performing physical exams, and evaluating changes in vital signs from baseline, routine serum chemistry, hematology results and coagulation profileOverall survival, defined as the time from the start of treatment to the date of death due to any causeEvent-free survival, defined as the time from start of treatment to the date of hematologic disease

Objective(s)	Endpoint(s)
	relapse/progression, graft failure, or death due to any cause

• To assess Failure-Free Survival (FFS)	
• Failure-free survival, defined as the time from the start of treatment to date of hematologic disease relapse/progression, non-relapse mortality, or addition of new systemic aGvHD treatment

• To assess Non Relapse Mortality (NRM)	
• Non-relapse mortality (NRM), defined as the time from start of treatment to date of death not preceded by hematologic disease relapse/progression

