3. ***post-treatment period***: starting at day 31 after last administration of ruxolitinib.

Safety summaries (tables, figures) include only data from the on-treatment period with the exception of baseline data which will also be summarized where appropriate (e.g. change from baseline summaries). In addition, a separate summary for death including on-treatment and post-treatment deaths will be provided. In particular, summary tables for adverse events (AEs) will summarize only on-treatment events, with a start date during the on-treatment period (***treatment-emergent*** AEs).

However, all safety data (including those from the post-treatment period) will be listed and those collected during the pre-treatment and post-treatment period will be flagged.

Windows for multiple assessments

In order to summarize data collected over time (including unscheduled visits), the assessments will be time slotted. The following general rule will be applied in creating the assessment windows: If more than one assessment is done within the same time window, the assessment performed closest to the target date will be used. If two assessments within a time window are equidistant from the target date, then the earlier of the two assessments will be used. If multiple assessments on the same date then the worst case will be used. Data from all assessments (scheduled and unscheduled), including multiple assessments, will be listed.

The following time windows are defined for descriptive summaries on aGvHD assessment, biomarkers and safety ([Table 2-1](#)) by visit. The end of treatment assessment will be mapped into the time points as appropriate.

Table 2-1 Time windows for aGvHD assessment, [REDACTED] and safety assessment (lab, vital sign, growth, etc.)

Time Window	Planned Visit Timing	Time Window Definition
-------------	----------------------	------------------------

On treatment

Baseline (Day 1)	On or before Study Day 1	≤ Study Day 1
Week 1	Study Day 7	Study Days 4 – 10
Week 2	Study Day 14	Study Days 11 – 17
Week 3	Study Day 21	Study Days 18 – 24
Week 4	Study Day 28	Study Days 25 – 31
Week 5	Study Day 35	Study Days 32 – 38
Week 6	Study Day 42	Study Days 39 – 45
Week 7	Study Day 49	Study Days 46 – 52
Week 8	Study Day 56	Study Days 53 – 59
Week 12	Study Day 84	Study Days 71 – 98
Week 16	Study Day 112	Study Days 99 – 126
Week 20	Study Day 140	Study Days 127 – 154
Week 24	Study Day 168	Study Days 155 – 182
Week 28	Study Day 196	Study Days 183 – 210

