3.8 Safety analyses

For all safety analyses, the safety set will be used. All listings and tables will be presented by group. If the Phase I starting dose is different to RP2D, the safety data will be listed and summarized by age group and dose level. For safety evaluations (except for AE), the last available assessment on or before the date of start of study treatment is taken as the “baseline” assessment.

Safety summaries (tables, figures) include only data from the on-treatment period with the exception of baseline data which will also be summarized where appropriate (e.g. change from baseline summaries). In addition, a separate summary for death including on treatment and post treatment deaths will be provided. In particular, summary tables for (AEs) will summarize only on-treatment events, with a start date during the on-treatment period (*treatment-emergent* AEs).

The on-treatment period lasts from the date of first administration of ruxolitinib to 30 days after the date of the last actual administration of ruxolitinib.

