3.8.1.1 Adverse events of special interest / grouping of AEs

[REDACTED]

For each AESI, number and percentage of patients with at least one event of the AESI occurring during on-treatment period will be summarized. Summaries of AESIs will be provided by group (specifying grade, SAE, relationship, leading to treatment discontinuation, leading to dose adjustment/interruption, hospitalization, death etc.).

A listing of all grouping levels down to the MedDRA preferred terms used to define each AESI will be generated.

In addition to summarizing infections by CTCAE grade, they will also be summarized using infection severity (protocol Appendix 1) for the on-treatment period. A listing of infection with infection severity will be generated and the events with start date outside of on-treatment period will be flagged.

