3.8.4.3 Cumulative incidence of grade 3 infection

Cumulative incidence curves for time to grade ≥ 3 infections as well as estimates at 1, 2, 6 months etc. with 95% confidence intervals will be presented overall and for each age group (if sufficient number of patients are available in the age groups) as well as by treatment-naïve vs SR-cGvHD, considering death or discontinuation from study treatment (due to any reason) without prior infection as competing risks.

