Sample size	Minimum No. of responders	Response Rate	Probability to have a 90% CI with lower limit $\geq 60\%$	90% CI	
37	28	0.76	0.809	0.614	0.867
38	29	0.76	0.784	0.623	0.871
39	29	0.74	0.859	0.604	0.854
40	30	0.75	0.839	0.613	0.858
41	31	0.76	0.818	0.621	0.861
42	31	0.74	0.882	0.604	0.846
43	32	0.74	0.864	0.612	0.849
44	33	0.75	0.846	0.620	0.853
45	33	0.73	0.901	0.604	0.838
46	34	0.74	0.886	0.612	0.842
47	35	0.74	0.869	0.619	0.846
48	35	0.73	0.916	0.604	0.832
49	36	0.73	0.903	0.612	0.835
50	37	0.74	0.889	0.619	0.838

5 Change to protocol specified analyses

No change from protocol

6 Appendix

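### Two protocol safety summaries lose their own time windows in the SAP: Grade 2 to 3 infections over Day 1 to 56, and second primary malignancies over the whole study

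*Protocol*

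**What the plan says.** **Protocol 12.5.2 (Safety endpoints)** restricts safety summaries to the on-treatment period, apart from baseline data and a separate death summary. Later in the same section it sets two specific windows:
- Grade 2 to 3 infections, graded by the Appendix 1 severity scale, "during the aGvHD treatment period Day 1 to Day 56 will be summarized in addition to standard CTCAE grading".
- For second cancers, the "proportion of patients developing second primary malignancies will be summarized based on the entire study period".

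**SAP 3.1.1 and 3.8** carry the general rule over: "Safety summaries (tables, figures) include only data from the on-treatment period with the exception of baseline data". The separate death summary is the only other exception named. The on-treatment period runs "from the date of first administration of ruxolitinib to 30 days after the date of the last actual administration of ruxolitinib". Safety data from outside it are listed and flagged.

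**SAP 3.8.1.1** says of infections that, besides CTCAE grade, "they will also be summarized using infection severity (protocol Appendix 1) for the on-treatment period". It gives neither a Day 1 to 56 window nor a Grade 2 to 3 proportion.

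**SAP 2.3** names second malignancies within the safety endpoint ("Adverse Events including occurrence of any second primary malignancies, infections"). They appear again in 3.1.1 as a source for the last contact date. No summary of them is visible.

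**SAP Section 5** reads: "No change from protocol".

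**The concern.** A specific instruction that follows a general rule in the same section is normally read as an exception to it. The protocol therefore asks for two proportions that the SAP, as visible, does not produce.

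Second malignancies are late events. Protocol 3.3 gives them as one reason for long-term follow-up. Table 8-1 schedules the assessment at Months 12, 18 and 24, and Protocol 8.5.4.8 has them monitored to 24 months and reported as adverse events. Protocol 4.5 intends to compare the rates with epidemiologic data. That comparison needs a summarised whole-study figure, and an on-treatment table would miss most of the period in which such events are expected.

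For infections, a window of fixed length becomes one set by how long each patient stays on ruxolitinib. Protocol 6.1.5 requires patients without a response at Day 28 to stop, so the window length depends partly on response. A crude proportion over it is harder to interpret than one over a common 56 days.

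**Working it through.** The plan gives no figure of its own to reproduce here, so the check is a comparison of windows followed by day arithmetic.

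**Inputs**
- End of on-treatment period: last dose day plus 30 (SAP 3.1.1 and 3.8).
- Protocol infection window: Day 1 to Day 56 (Protocol 12.5.2).
- End of malignancy follow-up: Month 24, target Study Day 730 (SAP 3.1.1, time-window table).
- Planned treatment: 24 weeks, Day 168 (Protocol 6.1.5). Maximum: 48 weeks, Day 336 (Protocol 3.3).
- Non-responders stop at Day 28 (Protocol 6.1.5).

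**Formulas**, with L the last dose day: E = L + 30 is the last on-treatment day; E − 56 is the difference from the protocol infection window; 730 − E is the malignancy follow-up outside an on-treatment table.

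| L | E | Against Day 56 | 730 − E | Share of 730 |
|---|---|---|---|---|
| 10 | 40 | 16 days short | 690 | 94.5% |
| 25 | 55 | 1 day short | 675 | 92.5% |
| 26 | 56 | equal | 674 | 92.3% |
| 28 | 58 | 2 days beyond | 672 | 92.1% |
| 168 | 198 | 142 days beyond | 532 | 72.9% |
| 336 | 366 | 310 days beyond | 364 | 49.9% |

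**Malignancies.** After the planned 24 weeks the on-treatment period covers 198 of 730 days. The 532 days left out are about 17.5 months (532 / 30.4375, the SAP's month length). The best case, treatment to Week 48, covers 366 of 730 days.

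**Infections.** The SAP window is shorter than the protocol's for any last dose before Day 26, and longer for any after it.

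**Does another SAP analysis fill the gap?** SAP 3.8.4.3 plans "Cumulative incidence curves for time to grade ≥ 3 infections as well as estimates at 1, 2, 6 months etc", with death and treatment discontinuation as competing risks. Its 2-month estimate falls at about Day 61 (2 × 30.4375 = 60.9), close to Day 56. But it leaves out Grade 2, and an infection that follows discontinuation is not counted because the competing event came first. It does not reproduce the protocol's Grade 2 to 3 proportion.

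**The case against.** Several points on the other side stand.

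- **The on-treatment rule is not the SAP's invention.** A reader might infer that a blanket SAP rule overrides the protocol. The same rule, and the on-treatment limit on summaries of adverse events of special interest, are already in Protocol 12.5.2. The difference is that the SAP keeps the rule and does not carry over the two exceptions.
- **The two halves differ in strength.** The infection window is changed by an explicit SAP sentence. The malignancy summary is simply not visible, and the SAP is partly redacted, including the opening of 3.8.1.1. Nothing shows that the summary was deliberately withdrawn. The redaction does not settle the matter in the SAP's favour, though: the visible text limits every summary of events of special interest to the on-treatment period, so listing second malignancies there would not restore the whole-study window.
- **Late malignancies would not vanish.** SAP 3.8.2 tabulates all deaths, including post-treatment deaths, by system organ class and preferred term. Fatal cases are therefore summarised, and non-fatal post-treatment cases appear in flagged listings. With 45 patients they could be counted by hand.
- **Confounded comparisons between diagnoses are not shown.** Safety is descriptive, and the diagnosis subgroup tables in SAP 3.2.1 do not include the infection-severity summary. The supportable point is narrower: a window that varies with time on drug makes the crude proportion harder to read.
- **Restoring Day 1 to 56 is not entirely free.** Table 8-1 collects adverse events until the safety follow-up visit, and Protocol 10.1.1 requires at least 30 days after the last dose. For patients stopping before about Day 26, infection data to Day 56 may be incomplete, and a plain proportion would count unobserved days as infection-free.

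**Conclusion.** The point holds as a protocol-to-SAP inconsistency. One window is explicitly changed, one whole-study summary is absent from the visible SAP, and Section 5 reports no departure. Followed as written, the on-treatment rule leaves 73% of the 730-day malignancy follow-up outside the tables after 24 weeks of treatment and 50% after 48 weeks. It also replaces a fixed 56-day infection window with one ending anywhere from before Day 56 up to Day 366.

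These figures assume follow-up to the Month 24 target day, treatment ending by Day 336, and no whole-study malignancy table in the redacted text. The consequence is modest: no efficacy estimate is affected and no safety data are lost. What is missing is two summarised proportions that the protocol promised, one of which it intends to set against epidemiologic rates.

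**What to change.** In SAP 3.8, add two named exceptions to the on-treatment rule:

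1. Proportion of patients with a second primary malignancy, Day 1 to Month 24.
2. Proportion of patients with a Grade 2 to 3 infection by Appendix 1 severity, Day 1 to Day 56. Either report beside it the number of patients whose adverse event collection ended before Day 56, or give a cumulative-incidence estimate at Day 56 that censors at the end of adverse event collection and treats death as a competing risk. Censoring assumes that patients no longer under collection have the same infection risk as those who are, which may fail for early stoppers, so the count is worth showing in either case.

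Keep the on-treatment infection-severity table as an additional output. If either departure is intended, record it with its reason in SAP Section 5.

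The cost is two small tables. The malignancy assessments are already scheduled to Month 24. The infection table uses adverse events already collected, subject to the early-stopper gap, and needs no new visits.

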12.5.3 Other endpoints

Acceptability and Palatability assessment

All acceptability and palatability assessment data will be listed by group and patient for all patients on safety analysis set.

12.5.4 Pharmacokinetics

In patients with extensive PK sampling on Day 1 (samples 1 to 8 described in [Section 8.6.1.1](#)), PK parameters of ruxolitinib will be calculated by non-compartmental methods using Phoenix WinNonlin (Pharsight, Mountain View, CA) software. Additional PK parameters may be estimated as needed. The following parameters will be calculated ([Table 12-1](#)).

Table 12-1 Non-compartmental pharmacokinetic parameters of ruxolitinib

AUClast	The AUC from time zero to the last measurable concentration sampling time (Tlast)
AUCinf	The AUC from time zero extrapolated to infinity
AUC0-12	The AUC from time zero extrapolated to 12 hours
Cmax	The maximum (peak) observed plasma drug concentration
Ctrough	The minimum observed plasma concentration at the end of an administration interval (corresponding to the pre-dose concentration prior to the following administration)
Tmax	The time to reach maximum (peak) plasma, blood, serum, or other body fluid drug concentration after single dose administration (time)
T1/2	The elimination half-life associated with the terminal slope (Lambda_z) of a semi logarithmic concentration-time curve
CL/F	The total body clearance of drug from the plasma
Vz/F	The apparent volume of distribution during terminal phase (associated with Lambda_z)

Plasma concentrations obtained from the sparse sampling schedules (described in [Section 8.6.1.1](#)) will be analyzed using a population PK approach along with data obtained in the Phase I.

Statistical methods for pharmacokinetic analyses

Ruxolitinib concentrations data will be listed by group. Descriptive summary statistics will be provided by group at each scheduled time point. Summary statistics will include n (number of patients with non-missing values), mean (arithmetic and geometric), SD, CV (arithmetic and geometric), median, minimum and maximum. Individual profiles with median by dose level as well as arithmetic mean with SD and geometric mean ruxolitinib plasma concentration versus time profiles by treatment will be displayed graphically.

Ruxolitinib plasma PK parameters data will be listed by group. Descriptive statistics (n, arithmetic mean, standard deviation (SD), coefficient of variation (CV)% for mean, geometric mean, geometric CV%, median, minimum and maximum) will be provided for all PK parameters by dose level except for Tmax where median, minimum and maximum will be presented.

If the Phase I preliminary dose is different to RP2D, PK data will be listed and summarized by age group and dose level.

Population PK approach on pooled Phase I and Phase II data

Concentration results from the sparse sampling performed in the Phase II will be added to those from Phase I and analyzed further using nonlinear mixed effects modeling (population PK) or other model-based approaches, as appropriate. Details of the analysis method will be developed in a PK analysis plan and the population PK analysis will be documented in a separate report.

During modeling of the pharmacokinetics of study treatment, the broad principles outlined in the FDA guidance will be followed (Guidance for Industry: Population Pharmacokinetics Fed 1999).

Exposure-Response analysis

A detailed description of exposure-response analysis will be developed in the analysis plan. Briefly, the objectives are to:

[figure not shown]
- Characterize the exposure-efficacy relationship of ruxolitinib with efficacy response defined as overall response rate at Day 28, durable response at Day 56, and Overall survival. Exposure metrics will be described in further details in the analysis plan.
- Characterize the exposure-safety relationship of ruxolitinib with safety response defined as 1st occurrence AEs, 1st occurrence of G3/4 AEs, 1st occurrence of AEs of interest, and appropriate liver function parameters. Exposure metrics will be described in further details in the SAP.
- Exposure-Biomarker – [REDACTED]

[figure not shown]
Average steady-state exposures and/or other PK parameters for the population may be computed by the population PK model accounting for dose modifications or dose interruptions up to the day prior to the day of assessments. Population PK derived parameters may be used for exposure-response analysis by appropriate methods.

Data handling principles

Plasma concentration values below the limit of quantification (BLQ) will be set to zero by the Bioanalyst, and will be displayed as zero in the listings and flagged. BLQ values will be treated as zero in any calculations of summary statistics, and treated as missing for the calculation of the geometric means and their coefficient of variation (CV%).

Any missing PK parameter or concentration will not be imputed.

